# **STUDY TITLE:**

# Comparison of Intraoperative Heart Rate and Respiratory Rate Acquired Via ATLASense Raphael PolyMonitor and Standard Intraoperative Monitors

### 1. STUDY AIM, BACKGROUND, AND DESIGN ABSTRACT

Vital signs are the objective foundation by which health care providers base clinical decisions. Thus, changes in vital signs serve as an important indicator of physiologic decline. To efficiently monitor for patient deterioration, we may benefit from technical innovation which improves upon traditional surveillance and reporting of these critical patient values. New remote monitoring technologies offer a method of obtaining continuous and comprehensive surveillance of patient vital signs, which can be transmitted to a remote working station for display and analysis . Indeed, investigation into the accuracy of wireless monitoring devices in reporting key parameters such as heart rate (HR) and respiratory rate (RR) as compared to traditional monitoring have shown some promising results .

The ATLASense RAPHAEL PolyMonitor is an investigational wearable and wireless patient monitoring device. The monitor can be attached to a patient's chest, and collect continuous physiological signals including HR, RR, skin temperature, body movement, as well as non-invasive blood pressure (NIBP) and transmit this information remotely for display and analysis. Ultimately, this PolyMonitor may be able to process multiple physiologic signals simultaneously for early detection and predictive modeling of patient physiologic deterioration, change the way alerts are transmitted to clinicians, reduce infection risk of multiple monitors reused on patients, and extend perioperative physiologic monitoring beyond the operating room and recovery areas to a patients home. While this monitor has significant potential to improve the efficiency of patient monitoring, it has yet to undergo validation studies.

In this observational comparison study, we aim to compare the HR and respiratory RR of intraoperative surgical patients simultaneously recorded by standard intraoperative monitors and the ATLASense RAPHAEL PolyMonitor. We also aim to determine degree of data loss, data gap duration, and validate the PolyMonitor alert system for tachycardia and bradycardia. Additional parameters of non-invasive blood pressure (NIBP) and body temperature will also be compared between the PolyMonitor and standard intraoperative

monitors. Finally, this study will provide insight into the logistics of intraoperative use of the PolyMonitor.

The ATLASense Raphael PolyMonitor will be placed on the patient's left chest mid sternal line in the operating room. Traditional physiologic monitors described above will also be placed on the patient in the operating room. Data will be collected via the ATLASense system and through the traditional operating room monitors, and this data will be time matched through synchronization of the monitors post hoc. The time matched data pairs will undergo statistical analysis post hoc.

We anticipate that this study will validate the intraoperative HR and RR measured through the ATLASense Raphael PolyMonitor, providing adequate data points for statistical analysis with 95% limits of agreement, bias, and data loss/gaps. Success is also the logistical lessons learned for using this monitor in the intraoperative setting.

This study will provide a foundation for further investigation into the use of the ATLASense Raphael PolyMonitor as a tool for early detection and predictive modeling of patient physiological deterioration. With further study, this device has the potential to replace multiple traditional monitors, provide individualized data capture to build a predictive model for each patient and may extend perioperative physiologic monitoring beyond the operating room and recovery areas to a patient's home.

# 2. SUBJECT POPULATION AND ELIGIBILITY

#### Subject Population:

Adult patients who are scheduled to undergo general anesthesia during their elective surgery at Henry Ford Hospital - Main Campus between October 2021 and December 2021.

#### Inclusion criteria:

English speaking Adult males or females (above the age of 18) Scheduled to undergo general anesthesia during elective surgery

#### Exclusion criteria:

Pregnant adult female

Thoracic surgery Left lateral decubitus positioning required during procedure Surgery involving the left flank, or requiring surgical field involving the left flank Surgery involving the left chest, or requiring surgical field involving the left chest Allergy to adhesives Open wound, rash, or sore involving the left chest Presence of cardiac defibrillator, or pacemaker

# Enrollment

The electronic medical record available of subjects scheduled for elective procedures at Henry Ford Hospital – Main Campus will be reviewed by the study team to screen subjects for eligibility. Minimal necessary variables that need to be obtained include: age, gender, pregnancy status, BMI, planned procedure, associated diagnosis, allergies, and co-morbidities (Hypertension, Congestive Heart Failure, Chronic Obstructive Pulmonary Disease, Diabetes Mellitus, ASA status). Subjects will be called via telephone at least one week prior to their procedure to briefly introduce the study to them. For in-patients, it is possible that a study team member will visit their location in the hospital to introduce the study and review the Informed Consent Form with them in the week prior to their surgery. If interested, they will be sent the Informed Consent Form via email or mail (whatever their preference) to ensure that they have adequate time to read the consent form and ask questions. Patients will be consented in person prior to their elective procedure and given a copy of the signed consent form.

# 3. STUDY PROCEDURES

#### Study Design and Outcomes

This will be a prospective observational study comparing HR and RR of intraoperative surgical patients simultaneously recorded by standard intraoperative monitors and the ATLASense RAPHAEL PolyMonitor. Funding for this study will be provided internally. This study will fall under regulatory oversight by the FDA.

This study will consist of an initial chart review of patients scheduled to undergo elective procedures at Henry Ford Hospital – Main Campus from October 2021, to December 2021. The study team will review their medical record in EPIC prior to their scheduled procedure and screen them to ensure that they meet all eligibility requirements. Patients will be contacted at least one week prior to their scheduled

procedure to provide them with a brief introduction to the study. If they are interested, they will be sent an Informed Consent Form via mail or email (whichever is their preference). This will ensure that the patients have adequate time to review the consent form and ask questions prior to their procedure. They will then be consented in person prior to their procedure and given a copy of the signed consent form.

Our **primary study aim** is to determine if the ATLASense RAPHAEL PolyMonitor can reliably measure intraoperative HR and RR as compared to traditional intraoperative monitors. In order to evaluate this aim, our primary outcome will be bias and precision (95% limits of agreement) of HR and RR of the PolyMonitor compared with the traditional monitors. It is hypothesized that the ATLASense RAPHAEL PolyMonitor will provide HR and RR measurements within ± 10% of the reference monitor or ± 3 breaths/min or ± 5 beats/min .

A secondary outcome that will examined include technical reliability in terms of data loss occurrences, and data gap duration. Additional secondary outcomes include reliability in detecting bradycardia and tachycardia, as well as bias and precision (95% limits of agreement) of skin temperature and NIBP of the PolyMonitor compared with traditional monitors.

Further lessons include the logistics of employing this PolyMonitor in intraoperative setting including device placement, surgical practices that may impede data collection (body placement, etc), device placement, patient feedback on wearable, and patient positioning considerations.

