#### **Data Collection**

The information that will be pulled from patient charts in EPIC is as follows:

Age Gender Race Height Weight Pregnancy status BMI Planned surgery and associated diagnosis Allergies

Co-morbidities ASA status

On the day of surgery, the ATLASense RAPHAEL PolyMonitor will be placed on the patient's left chest mid sternal line in the operating room by the anesthesia provider. Traditional physiologic monitors including the GE E-PSMP-00 Monitor/Datex Ohmeda Aisys CS2: EKG HR, Ventilator RR, End Tidal CO2 RR, blood pressure cuff, \*\*\* core temperature probe will also be placed on the patient in the operating room.

Data acquisition will include: HR, RR, NIBP, core body temperature, data loss events (instances when data was not recorded/saved for any reason by the polymonitor or other monitors) and duration of data gaps, bradycardic events, and tachycardic events. Acquisition of data from the ATLASense PolyMonitor will be confirmed after the device is applied. Data will initially by tracked via medical record number (MRN). Following data acquisition, subjects will be deidentified using a random number generator to assign data sets for further data tracking.

Data will be collected via the ATLASense system and through the traditional operating room monitors, and this data will be time matched through synchronization of the monitors post hoc. Data collection intervals will be every 1 minute starting prior to induction of anesthesia and ending at the time of intraoperative monitor removal in the operating room. The ATLASense PolyMonitor will be removed at the same time as traditional physiologic monitors.

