### GE Alsys CS2™ - RR Detection

The Aisys CS2 is functionally integrated ventilation, respiratory monitoring, and breathing system. Module bays allow for the physical integration of legacy Datex-Ohmeda patient monitors and supports mounting of other GE Healthcare monitors, including the CARESCAPE™ Monitor B850. The Aisys CS2 Anesthesia System is intended to provide general inhalation anesthesia and ventilatory support to a wide range of patients. Respiratory rate is calculated with this system from the frequency of peak (end tidal) CO2 measurements per minute. A breath is defined as a change in the CO2 signal that exceeds 1% (8 mmHg). All concentrations are measured and displayed breath by breath.

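### RR is judged only by bias and limits of agreement under general anesthesia; if reference RR varies little, these cannot show that the PolyMonitor tracks RR

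*Combined protocol and SAP*

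**What the plan says.** - **Aim.** Section 3 (Study Design and Outcomes) sets the primary aim as to "determine if the ATLASense RAPHAEL PolyMonitor can reliably measure intraoperative HR and RR as compared to traditional intraoperative monitors".
- **Population.** Section 2 (Subject Population) enrolls "Adult patients who are scheduled to undergo general anesthesia during their elective surgery". Ventilation mode is neither an eligibility condition nor among the data items listed for collection.
- **Reference RR.** Section 3 (Data Collection) lists "EKG HR, Ventilator RR, End Tidal CO2 RR" among the traditional monitors. The Aisys CS2 section describes that system as "intended to provide general inhalation anesthesia and ventilatory support to a wide range of patients" and derives RR from end-tidal CO2 peaks.
- **Hypothesis.** Section 3 (Study Design and Outcomes) expects HR and RR readings "within ± 10% of the reference monitor or ± 3 breaths/min or ± 5 beats/min".
- **Analysis.** Section 3 (Statistical Analysis) plans repeated-measures Bland-Altman bias and limits of agreement for HR and RR. HR gets a second evaluation through sensitivity and specificity of the tachycardia and bradycardia alerts. RR gets none.
- **Recording window.** Pairs are taken each minute from before induction until the monitors come off (Data Collection).
- **Intended conclusion.** Section 1 states: "We anticipate that this study will validate the intraoperative HR and RR measured through the ATLASense Raphael PolyMonitor". Section 5 also speaks of validation. Section 1 presents the result as a base for later work on early detection of deterioration.

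**The concern.** Limits of agreement describe how far two readings lie apart. They do not ask whether the readings move together. Over a wide range the two questions nearly coincide, because a device that fails to follow the reference produces large differences. Over a narrow range they separate: a device that reports roughly the usual rate can look accurate without responding to breathing at all.

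Under general anesthesia, with RR read from an anesthesia ventilation system, a narrow range is plausible for at least part of each case. RR is half of the primary aim, and Section 1 itself treats change in vital signs as the signal of interest. A positive RR result could therefore be reported without evidence that the device responds to change.

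HR is much less exposed. A constant HR output would meet ±5 beats/min at zero bias only if the SD of HR were at most 5/1.96 = 2.55 beats/min, and the alert analysis tests HR separately.

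**Working it through.** **The plan's own figures.** The plan targets 14,303 pairs, about 238 hours, from 60-70 patients (Project Timeline). 14,303/60 = 238.4 h, which agrees. Per patient this is 238.4/70 = 3.4 h to 238.4/60 = 4.0 h. The 14,303 itself cannot be rebuilt, because no SD of differences or target precision is given for the agreement aim. The number of pairs does not affect the point below: more pairs estimate the limits more precisely but do not make them informative about tracking.

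**Break-even for a constant output.** Let the device always report c. Each difference is c − RR, so the SD of differences equals the total SD of reference RR:

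total SD = √(between-patient SD² + within-patient SD²)

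The limits are bias ± 1.96 × total SD. Both lie within ±3 when total SD ≤ (3 − |bias|)/1.96:

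- bias 0: 3/1.96 = 1.53
- bias 0.5: 2.5/1.96 = 1.28
- bias 1.0: 2/1.96 = 1.02

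This takes the ±3 branch of the hypothesis, which is the wider one at any rate below 3/0.10 = 30 breaths/min. At an assumed rate of 12, ±10% is ±1.2, and the zero-bias break-even falls to 1.2/1.96 = 0.61.

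**Range of assumed spreads.** The documents give no RR spread, so every SD here is an assumption (breaths/min; constant output 12, mean reference 12).

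| Between / within SD | Total SD | Limits | Within ±3? |
|---|---|---|---|
| 0.5 / 0.25 | 0.56 | ±1.1 | yes |
| 1 / 0.5 | 1.12 | ±2.2 | yes |
| 1 / 1 | 1.41 | ±2.8 | yes |
| 1.5 / 0.5 | 1.58 | ±3.1 | no |
| 2 / 0.5 | 2.06 | ±4.0 | no |
| 3 / 1 | 3.16 | ±6.2 | no |

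A simulation of the repeated-measures method (65 patients, 220 minutes each) agrees with these limits to within 0.1.

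**Adding more variable minutes.** Suppose a fraction f of minutes, around induction and emergence, has mean 16 and SD 4 (assumed). Then bias = −4f, and

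variance = (1 − f) × SD₀² + f × 4² + f(1 − f) × (16 − 12)²

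- f = 0.05, SDs 0.5/0.25: 0.297 + 0.80 + 0.76 = 1.857; SD 1.36; limits −2.87 to 2.47 (inside).
- f = 0.05, SDs 1/0.5: 1.188 + 0.80 + 0.76 = 2.748; SD 1.66; limits −3.45 to 3.05 (outside).
- f = 0.10, SDs 0.5/0.25: 0.281 + 1.60 + 1.44 = 3.321; SD 1.82; limits −3.97 to 3.17 (outside).

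At 3.4-4.0 h per patient, 5% is about 10-12 minutes.

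**A less extreme failure.** A device that gets each patient's average rate right but never follows changes has zero-bias limits of ±1.96 × within-patient SD, whatever the between-patient SD. With an assumed within-patient SD of 0.5, that is ±0.98.

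**The case against.** The strongest reply is that the premise is not in the documents. General anesthesia is required, but controlled ventilation is not stated, and no RR range or SD appears. Steady RR within a patient is also not enough for a stuck device to pass: the pooled limits include between-patient variance, and the stuck value must sit near the cohort mean. Half of the tabulated spreads make it fail. The recording window brings in minutes when RR need not be a machine setting, and under the assumptions shown 5-10% of these can be enough to push a stuck device outside ±3. The margin is stated as a hypothesis with an ambiguous *or*, and no rule ties the limits to it. Nothing suggests that the device gives a constant output; its RR section describes three independent respiration measures.

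All of this stands, and it makes the risk conditional. It does not remove the risk, because nothing in the plan would show a reader which case had occurred. The number of variable minutes that will yield usable pairs is not stated, and the device algorithm drops segments with motion artifact or irregular patterns, so the most informative minutes may be thinned. Between-patient variance also gives no protection against a device that has each patient's average right but misses changes.

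A reader might infer more: that the ventilator fixes RR in every case, so the study will validate a device that cannot measure breathing. The documents do not support that. They state neither a constant RR nor a pass rule, and Section 1 calls for further study before wider use.

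**Conclusion.** The gap is real but conditional. As planned, bias and limits of agreement are the only evidence on RR, and they cannot distinguish tracking from non-tracking if total reference SD is about 1.5 breaths/min or less. That threshold assumes the ±3 reading and zero bias; it tightens with bias, and to about 0.6 under the ±10% reading at a rate of 12. Whether the study will fall below it cannot be determined from the documents. The point does not undermine the agreement analysis itself. It limits what that analysis can support: closeness of readings over the RR range seen, not the ability to follow change. It should be settled before analysis, because it affects half of the primary aim and can be addressed with data the study already collects.

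**What to change.** 1. **Statistical Analysis, description of the reference.** Report the range of reference RR and its between- and within-patient SD. Beside the PolyMonitor limits, show the constant-output limits (±1.96 × total SD) as a descriptive benchmark only. They should not be an acceptance rule: with a reference SD of 0.5 they are ±0.98, and a device whose limits equaled its reported ±1 breath/min accuracy would be rejected although well inside ±3.
2. **Statistical Analysis, tracking.** Over all paired minutes, regress the PolyMonitor deviation from the patient's mean on the reference deviation from the patient's mean. Report the slope and the repeated-measures correlation with patient-clustered confidence intervals. Report limits of agreement separately for minutes with stable and with changing reference RR, with the definition fixed before the data are seen. Using all minutes for the main tracking estimate avoids selecting minutes on reference error.
3. **Section 1, conclusion.** Limit the RR conclusion to the range observed, and do not claim that RR changes are tracked unless item 2 supports it.

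Cost: analysis-plan wording and added analyses, with no new subjects or procedures. The RR claim may be narrower. If few RR changes occur, the tracking estimate will be imprecise, and error in the reference will pull the slope toward zero; the report should say so.

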#### **Data Collection**

The information that will be pulled from patient charts in EPIC is as follows:

Age Gender Race Height Weight Pregnancy status BMI Planned surgery and associated diagnosis Allergies

Co-morbidities ASA status

On the day of surgery, the ATLASense RAPHAEL PolyMonitor will be placed on the patient's left chest mid sternal line in the operating room by the anesthesia provider. Traditional physiologic monitors including the GE E-PSMP-00 Monitor/Datex Ohmeda Aisys CS2: EKG HR, Ventilator RR, End Tidal CO2 RR, blood pressure cuff, \*\*\* core temperature probe will also be placed on the patient in the operating room.

Data acquisition will include: HR, RR, NIBP, core body temperature, data loss events (instances when data was not recorded/saved for any reason by the polymonitor or other monitors) and duration of data gaps, bradycardic events, and tachycardic events. Acquisition of data from the ATLASense PolyMonitor will be confirmed after the device is applied. Data will initially by tracked via medical record number (MRN). Following data acquisition, subjects will be deidentified using a random number generator to assign data sets for further data tracking.

Data will be collected via the ATLASense system and through the traditional operating room monitors, and this data will be time matched through synchronization of the monitors post hoc. Data collection intervals will be every 1 minute starting prior to induction of anesthesia and ending at the time of intraoperative monitor removal in the operating room. The ATLASense PolyMonitor will be removed at the same time as traditional physiologic monitors.

# ATLASense RAPHAEL PolyMonitor

The ATLASense RAPHAEL PolyMonitor is a small, non-intrusive, wireless, wearable multi-sensor device, attached to the patient's torso either with adhesive disposable patch or as a smart shirt. It continuously collects multiple physiological signals, analyzes them and transmits them to the ATLASense server. The PolyMonitor is composed of a rechargeable lithium polymer battery (3.6 Volts, 370 milliamp hour), an independent charger (5 volt input via mini USB/USB cable) which employs a universal 90-240 VAC 50/60 Hz to 5VDC converter and four FDA-approved hydrogel electrodes. The device has safe fault limit on electrical current which exceeds regulatory requirements.

The system enables monitoring a multiple array of physiological, postural and emotional parameters. For this study, the Heart rate (HR) and Respiration rate (RR) derived parameters will be calculated and updated every second, stored in internal memory, and transmitted. Measurements and alerts are transmitted via a low-power radio protocol (BT 4.2 Low Energy) to hotspots ("gateways" connected to the hospital communication network). The data is sent to ATLASense central server and to the healthcare service provider's server connected with the electronic medical record.

# ATLASense RAPHAEL PolyMonitor – HR Detection

The electrocardiogram is recorded and processed to calculate the average HR by analyzing a single-lead electrocardiogram, which is preprocessed first to filter the raw electrocardiogram signal in order to minimize noise due to motion and muscle artifacts. Heart rate is measured using an algorithm developed by ATLASense.

The algorithm checks electrodes' contact to assure credibility, detects the R wave, computes several valid interbeat intervals, and computes the running HR with low latency. HR is calculated by computing inter-beat intervals (IBI), limiting IBI to one in every 300 mSec before the next beat (refractory period). The average HR is acquired by calculating the reciprocal of the average of 4 IBIs. Accuracy of resting HR is reported to be +/-1% or +/- 2 BPM, whichever is greater, and range of detection is reported to be from 30-240 BPM.

# ATLASense RAPHAEL PolyMonitor – RR Detection

The PolyMonitor incorporates three independent respiration measures for increased reliability: Piezoelectric respiration sensor with two, additionally derived respiration measures from two biopotential electrodes concurrently monitoring the torso ECG and EMG. The algorithm excludes from the calculation segments that are corrupted by motion artifacts or other irregular patterns. Accuracy of resting RR is reported to be +/- 5% or +/- 1 Breaths/Min, whichever is greater. A default RR alert is generated for no single breath in a 10 second period.

